7.2.2 Grade 3 Toxicities

Subjects will be required to permanently discontinue all study drugs for the following AEs:

- Any Grade 3 non-skin, drug-related AE lasting >7 days or recurs, with the following clarifications:
 - Grade 3 drug-related uveitis, pneumonitis, myocarditis, bronchospasm, hypersensitivity reaction, or infusion reaction of any duration requires discontinuation.
 - Grade 3 drug-related endocrinopathies, adequately controlled with only physiologic hormone replacement, do not require discontinuation. Adrenal insufficiency requires discontinuation regardless of control with hormone replacement.
 - Grade 3 drug-related laboratory abnormalities do not require treatment discontinuation except:
 - Grade ≥ 3 drug-related AST, ALT, or total bilirubin
 - Concurrent AST or ALT $>3x$ ULN and total bilirubin $>2x$ ULN

For any other Grade 3 treatment related non-hematologic toxicities, if the Grade 3 toxicity does not resolve to \leq Grade 1 within 21 days, all study therapy will be **permanently discontinued**.

7.2.3 Grade 4 Toxicities

If the patient experiences Grade 4 treatment related non-hematologic toxicity in either study cohort, all study therapy must be **permanently discontinued** regardless of the time to resolution \leq Grade 1 with the exception of the following instances:

- Grade 4 nausea or emesis which resolves to \leq Grade 1 within 7 days of optimal anti-emetic therapy.
 - Grade 4 endocrinopathies that can be mitigated with endocrine replacement with resolution to \leq Grade 1 within 7 days of initiating endocrine replacement therapy (i.e. hypothyroid, etc.).
-

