6.1.3 Name of Other Modality or Procedures

All patients enrolled in this trial will undergo a RC with bilateral (standard or extended) PLND as soon as possible but within 6 weeks of the last dose of neoadjuvant therapy as outlined above.

7. Dose Delays

All toxicities should be graded according to the National Cancer Institute (NCI) Common Terminology Criteria for Adverse Events Version 5.0 (CTCAE V5.0). A copy of the CTCAE V5.0 can be downloaded from the CTEP website (<http://www.ctep.cancer.gov>).

A +/-3 day window is allowed for scheduled therapy, required tests and/or visits except as otherwise noted. Delays due to holidays, weekends, bad weather or other unforeseen circumstances will be permitted.

Dose delays are not required for adverse events not deemed to be related to study treatment (i.e. events due to underlying disease) or for laboratory abnormalities not deemed to be clinically significant. Treat accordingly per institutional standards.

Any patient who cannot receive study therapy within 6 weeks from the previous dose in either cohort, will be permanently discontinued, except as noted below.

NO dose modifications will be allowed.

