7.2.1 Grade 1 and Grade 2 Toxicities

No dose interruptions will be performed for Grade 1 or 2 non-hematologic toxicities, except for:

- Any grade hypophysitis, meningitis, immune-related neurological AEs
- Any Grade 2 drug-related uveitis, eye pain, or blurred vision that does not respond to topical therapy and does not improve to Grade 1 severity within the retreatment period OR requires systemic treatment will require permanent discontinuation.
- Colitis (Grade 2)
- AST, ALT, bilirubin (Grade 2)
- Pneumonitis (Grade 2)
- Nephritis (Grade 2)

- Infusion reaction that does not resolve within an hour of stopping infusion (Section 7.3 for Infusion Reaction Guidelines), or
- Other intolerable or persistent Grade 2 drug-related AE, as per physician discretion.

Discontinue treatment for persistent Grade 2 immunologic AEs (such as colitis, pneumonitis, and nephritis) that do not recover to Grade 1 or resolve within 6 weeks after the last dose of study drug (Exceptions: rash, fatigue, amylase/lipase elevations, other electrolyte abnormalities).

In addition, discontinue treatment for persistent Grade 2 ALT, AST, or bilirubin that do not recover to Grade 1 or resolve within 6 weeks after the last dose of study drug. A thorough investigation of the cause of the ALT, AST, or total bilirubin elevation is recommended including the exclusion of other causes – e.g. concurrent medications, infection, injury, hypo-perfusion, and alcohol consumption. Close monitoring of hepatic labs at least weekly and consideration of imaging such as ultrasound of the liver is suggested.

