8.1 Study Duration

Patients will receive protocol therapy unless:

1. Disease progression per RECIST Version 1.1 criteria or clinical progression.
2. Toxicities considered unacceptable by either the patient or the investigator, despite optimal supportive care and dose delays.
3. Any requirement to discontinue based on dose delay guidelines in Section 7.1, Section 7.2, infusion reaction guidelines in Section 7.3 and Appendix III.
4. Development of an inter-current illness that prevents further administration of study treatment.
5. Extraordinary Medical Circumstances: If at any time the constraints of this protocol are detrimental to the patient's health, protocol treatment should be discontinued.
6. Patient withdraws consent or is unable to comply with study procedures.

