12.1.11 Side Effects

The overall safety experience with nivolumab is based on approximately 1500 subjects as either a monotherapy or in combination with other therapeutics. In general for monotherapy, the safety profile is similar across tumor types. The one exception is pulmonary inflammation AEs which may be numerically greater in subjects with Non-Small Cell Lung Cancer possibly because in some cases it can be difficult to distinguish between nivolumab-related and unrelated causes of pulmonary symptoms and radiographic changes. The most frequently reported treatment related AE is fatigue which is almost always low grade.

Most related AEs are thought to be due to the effects of inflammatory cells on specific tissues. The most common treatment-related adverse events seen in clinical trials of nivolumab included rash, pruritus, cough, peripheral edema, fatigue, arthralgias, upper respiratory tract infections, diarrhea and liver function test abnormalities. Additionally a number of patients experienced more severe autoimmune effects including immune-mediated pneumonitis, immune-mediated colitis, immune-mediated hepatitis, immune-mediated nephritis, immune-mediated encephalitis and immune-mediated endocrinopathies, such as adrenal insufficiency, hypothyroidism/hyperthyroidism and Type I Diabetes Mellitus. Less than 1% of patients in clinical trials experienced severe infusion reactions.

Nivolumab is a Pregnancy Category D drug.

Please refer to the Nivolumab IB and commercial package insert for full prescribing information.

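### Protocol Sections 7.2.2 and 7.2.3 do not settle whether Grade 4 adrenal insufficiency is always a stop; a short carve-out would

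*Protocol*

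**What the plan says.** Protocol Section 7.2 sets the rules for treatment-related non-hematologic toxicity under three headings, by grade.

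- **Section 7.2.2 (Grade 3).** A parent bullet on Grade 3 non-skin drug-related events is followed by clarifications. One of them begins: "Grade 3 drug-related endocrinopathies, adequately controlled with only physiologic hormone replacement, do not require discontinuation". Its next sentence is: "Adrenal insufficiency requires discontinuation regardless of control with hormone replacement". The second sentence gives no grade.
- **Section 7.2.3 (Grade 4).** Permanent discontinuation is the default, with two exceptions. The endocrine one covers "Grade 4 endocrinopathies that can be mitigated with endocrine replacement with resolution to" Grade 1 or lower, "within 7 days of initiating endocrine replacement therapy (i.e. hypothyroid, etc"). It does not mention adrenal insufficiency and does not refer back to 7.2.2.
- **Section 7.2.1 (Grades 1 and 2).** The rule is "No dose interruptions will be performed for Grade 1 or 2 non-hematologic toxicities, except for" a list of named events. Adrenal insufficiency is not on the list.
- **Section 8.1, item 3.** Therapy ends on "Any requirement to discontinue based on dose delay guidelines in Section 7.1, Section 7.2, infusion reaction guidelines in Section 7.3 and Appendix III".
- **Section 12.1.11.** Nivolumab's side effects include "immune-mediated endocrinopathies, such as adrenal insufficiency, hypothyroidism/hyperthyroidism and Type I Diabetes Mellitus".

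SAP Section 4.3.3 repeats parts of the stopping rules and does not mention adrenal insufficiency.

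**The concern.** Two rules meet at Grade 4 adrenal insufficiency, and neither refers to the other. One stops the drug even when hormone replacement controls the event. The other lifts the automatic stop because replacement controls the event. If each list is taken to apply only to the grade in its heading, adrenal insufficiency is a mandatory stop at Grade 3, while at Grade 4 it is not an automatic stop once it has resolved within 7 days. A rule that is looser for the more severe event is unlikely to be intended.

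What is at stake is patient safety ahead of major surgery, and consistent dosing across about 8 sites. The statistical analysis is not affected.

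**Working it through.** The protocol gives no figure on this point, so the check compares the text.

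**1. Does the Grade 4 exception reach adrenal insufficiency?** By its words, yes. The exception concerns endocrinopathies, Section 12.1.11 counts adrenal insufficiency as one, and the example list is left open.

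**2. Which grades does the 7.2.2 sentence cover?** Three readings are possible.

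| Reading of the 7.2.2 stop | Grades 1–2 | Grade 3 | Grade 4, resolved to Grade 1 or lower within 7 days | Fit with the rest of Section 7.2 |
|---|---|---|---|---|
| Every grade | Stop | Stop | Stop | Strains against 7.2.1, which does not name the event |
| Grade 3 and above | 7.2.1 applies | Stop | Stop | Consistent, and keeps the order of severity |
| Grade 3 only | 7.2.1 applies | Stop | No automatic stop | Consistent with the headings, but looser at Grade 4 than at Grade 3 |

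**3. Does the drafting style decide it?** Not fully. Where the drafters want a wider range they often say so: hypophysitis is marked as any grade in 7.2.1, and liver tests are marked Grade ≥ 3 in 7.2.2. The adrenal sentence has no such marker. Yet those same entries show that a list under a grade heading can hold rules reaching beyond that grade, and 7.2.2 also contains an ungraded stop for combined transaminase and bilirubin elevation.

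**4. Is adrenal insufficiency a special case?** Yes. The other events that 7.2.2 names as Grade 3 stops of any duration (uveitis, pneumonitis, myocarditis, bronchospasm, hypersensitivity and infusion reactions) meet the default stop at Grade 4. Adrenal insufficiency is the named Grade 3 stop that fits a Grade 4 exception.

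**5. Does timing close the path?** No. Dose 2 is due at week 4, and Section 7 says "Any patient who cannot receive study therapy within 6 weeks from the previous dose in either cohort, will be permanently discontinued". The outer limit is therefore 6 × 7 = 42 days after dose 1. Replacement started by day 42 − 7 = 35 leaves the full 7-day window.

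**6. Does another visible rule bar dose 2?** Not expressly. Section 7.4.1 permits adrenal replacement steroids in the absence of active autoimmune disease. Section 8.1 item 3 enforces whatever Section 7.2 and Appendix III require, but does not say which part of 7.2 prevails. The Appendix III endocrinopathy algorithm is not visible in this copy and could contain such a bar.

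**The case against.** The strongest reply is that the text, read as a whole, already stops the drug. The 7.2.2 sentence names the event and rules out control by replacement as a reason to continue. The 7.2.3 exception is general, rests on that same control, and names only hypothyroidism. It lifts the automatic Grade 4 stop; it neither authorises a dose nor cancels a separate and more specific stop that binds through Section 8.1. A reading of Grade 3 and above fits the heading and the order of severity, and leaves 7.2.1 untouched.

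Most of this stands. It makes Grade 3 and above the better reading, and it rules out two stronger claims that a reader might infer. One is that the protocol contradicts itself outright; it does not, because a natural reading reconciles the two sections. The other is that the protocol permits re-dosing after Grade 4 adrenal insufficiency; it does not say so, and Appendix III may forbid it. What remains is that the reconciliation is left to the site, because no visible sentence says which rule prevails.

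Safeguards also exist. A life-threatening event is serious under Section 9.2.1 and is reported to the sponsor within 24 hours under Section 9.3, so the sponsor would normally know before dose 2. An investigator can stop for unacceptable toxicity under Section 8.1 item 2. These make the path less likely, but the report is not a stopping rule and the second safeguard is a matter of judgement. Grade 3 or higher endocrine events also count in the interim safety review, but that review follows surgery in the patients concerned and so cannot protect dose 2 for the same patient.

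**Conclusion.** The concern holds as an ambiguity. A site reading by grade could treat dose 2 as allowed after Grade 4 adrenal insufficiency, although the same event at Grade 3 is a mandatory stop. The better reading closes this gap, and the wording should say so.

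The size per affected patient is at most one dosing visit, dose 2 of 2: one infusion in Cohort 1 and two in Cohort 2. Section 12.1.5 indicates that Cohort 1 has been dosed and Cohort 2 has begun, so a change would matter only for Cohort 2 patients who have not yet reached dose 2.

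The frequency is unknown. A reader might be tempted to derive one from the overall Grade 3–4 treatment-related rate in Section 1.6, but that figure does not separate adrenal insufficiency, so no rate should be quoted. The path also requires four things: resolution to Grade 1 or lower within 7 days, which depends on CTCAE v5.0 grading that the protocol does not reproduce; no bar in Appendix III; a site that reads by grade; and an investigator who chooses to re-dose. No estimate, power calculation or interim rule changes. The severity is low: the sponsor could make the change.

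**What to change.** Make two short wording edits at the next amendment, and one check.

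1. In 7.2.3, add to the endocrine exception that adrenal insufficiency is excluded from it and means permanent discontinuation whether or not replacement controls it.
2. In 7.2.2, put *Grade ≥ 3* at the start of the adrenal insufficiency sentence. If the sponsor meant every grade, write *any grade* there instead and add a matching entry to the 7.2.1 list, so that the edit does not loosen an intended stop.
3. Confirm that the Appendix III endocrinopathy algorithm says the same.

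No new procedure, data or patients are needed. The cost is that a patient whose Grade 4 adrenal insufficiency is rapidly controlled loses the option of dose 2, an outcome that 7.2.2 already imposes at Grade 3.

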7.3 Infusion Reaction Guidelines

Since nivolumab and lirilumab contain only human immunoglobulin protein sequences, each is unlikely to be immunogenic and induce an infusion or hypersensitivity reaction. However, if such a reaction were to occur, it might manifest with fever, chills, rigors, headache, rash, pruritus, arthralgias, hypo- or hypertension, bronchospasm, or other symptoms. All Grade 3 or 4 infusion reactions should be reported within 24 hours to PrECOG and reported as a serious adverse event (SAE) if criteria are met. Infusion reactions should be graded according to NCI CTCAE (Version 5.0) guidelines. Treatment recommendations are provided below and may be modified based on local treatment standards and guidelines as appropriate:

- For Grade 1 symptoms (Mild reaction; infusion interruption not indicated; intervention not indicated):

Remain at bedside and monitor subject until recovery from symptoms. The following prophylactic pre-medications are recommended for future infusions: diphenhydramine 50 mg (or equivalent) and/or paracetamol 325 to 1000 mg (acetaminophen) at least 30 minutes before additional nivolumab or lirilumab administrations.

- For Grade 2 symptoms (Moderate reaction requires therapy or infusion interruption but responds promptly to symptomatic treatment [e.g., antihistamines, non-steroidal anti-inflammatory drugs, narcotics, corticosteroids, bronchodilators, IV fluids]; prophylactic medications indicated for ≤ 24 hours):

Stop the nivolumab or lirilumab infusion, begin an IV infusion of normal saline (NS), and treat the subject with diphenhydramine 50 mg IV (or equivalent) and/or paracetamol 325 to 1000 mg (acetaminophen); remain at bedside and monitor subject until resolution of symptoms. Corticosteroid or bronchodilator therapy may also be administered as appropriate. If the infusion is interrupted, restart the infusion at 50% of the original infusion rate when symptoms resolve; if no further complications ensue after 30 minutes, the rate may be increased to 100% of the original infusion rate. Monitor subject closely. If symptoms recur then no further nivolumab or lirilumab will be administered at that visit. Administer diphenhydramine 50 mg IV, and remain at bedside and monitor the subject until resolution of symptoms. The amount of study drug infused must be recorded on the electronic case report form (eCRF). The following prophylactic pre-medications are recommended for future infusions: diphenhydramine 50 mg (or equivalent) and/or paracetamol 325 to 1000 mg (acetaminophen) should be administered at least 30 minutes before additional nivolumab or lirilumab administrations. If necessary, corticosteroids (recommended dose: up to 25 mg of IV hydrocortisone or equivalent) may be used.

- For Grade 3 or Grade 4 symptoms (Severe reaction, Grade 3: prolonged [i.e., not rapidly responsive to symptomatic medication and/or brief interruption of infusion]; recurrence of symptoms following initial improvement; hospitalization indicated for other clinical sequelae [e.g., renal impairment, pulmonary infiltrates]; Grade 4: (life threatening; pressor or ventilator support indicated):

Immediately discontinue infusion of nivolumab or lirilumab. Begin an IV infusion of NS, and treat the subject as follows. Recommend bronchodilators, epinephrine 0.2 to 1 mg of a 1:1,000 solution for subcutaneous administration or 0.1 to 0.25 mg of a 1:10,000 solution injected slowly for IV administration, and/or diphenhydramine 50 mg IV with methylprednisolone 100 mg IV (or equivalent), as needed. Subject should be monitored until the investigator is comfortable that the symptoms will not recur. Nivolumab or lirilumab will be permanently discontinued. Investigators should follow their institutional guidelines for the treatment of anaphylaxis. Remain at bedside and monitor subject until recovery from symptoms. In the case of late-occurring hypersensitivity symptoms (e.g.,

appearance of a localized or generalized pruritus within 1 week after treatment), symptomatic treatment may be given (e.g., oral antihistamine, or corticosteroids).

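### Protocol 7.3 lets symptoms that recur after an infusion restart be managed as Grade 2, with the week 4 dose left open, although its own Grade 3 wording and 7.2.2 require permanent discontinuation

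*Protocol*

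**What the plan says.** Protocol 7.3 manages infusion reactions by grade. It states that "Infusion reactions should be graded according to NCI CTCAE (Version 5.0) guidelines" and then prints its own description of each grade.

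- **Grade 1:** "Mild reaction; infusion interruption not indicated; intervention not indicated".
- **Grade 2:** "Moderate reaction requires therapy or infusion interruption", with a prompt response to symptomatic treatment. The infusion is stopped and the patient treated. If it was interrupted, the site is to "restart the infusion at 50% of the original infusion rate when symptoms resolve". Then: "If symptoms recur then no further nivolumab or lirilumab will be administered at that visit". After antihistamine, bedside monitoring and recording of the amount infused, the branch continues: "The following prophylactic pre-medications are recommended for future infusions".
- **Grade 3 or 4:** the Grade 3 description contains three features separated by semicolons: a prolonged reaction, "recurrence of symptoms following initial improvement", and hospitalization for sequelae. The action is permanent discontinuation.

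On reporting, 7.3 says: "All Grade 3 or 4 infusion reactions should be reported within 24 hours to PrECOG".

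Section 7.2.2 lists the events for which all study drugs must be stopped permanently. A drug-related Grade 3 infusion reaction is on that list regardless of how long it lasts. Section 8.1 item 3 ends protocol therapy whenever 7.1, 7.2 or 7.3 requires discontinuation.

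Sections 6.1 and 12.1.5 record that a few Cohort 2 patients reacted to nivolumab, were given steroids and resumed at 50%, after which the nivolumab infusion was lengthened to 60 minutes.

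**The concern.** The restart step and the Grade 3 description cover the same clinical sequence but lead to different dosing decisions. A patient reacts, settles, is restarted at a lower rate, and reacts again. Under the Grade 2 bullet the drug stops for the day, and the next written guidance concerns premedication before later doses. Under the Grade 3 bullet and 7.2.2 there are no later doses.

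What is at stake is mainly the patient's safety at week 4, together with sites treating like patients alike. A site that works down the Grade 2 bullet as printed could give a second dose to someone the protocol elsewhere requires to stop. The step is not academic, because sites have already used the restart pathway in Cohort 2.

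**Working it through.** The plan gives no figure to reproduce. The check sets the provisions side by side.

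1. **Entry to the Grade 2 branch.** The patient needs treatment or interruption and responds promptly. Symptoms resolve, and the infusion restarts at half rate.
2. **Symptoms return.** The Grade 2 bullet names this event and limits the stop to the current visit. It does not refer to the Grade 3 bullet.
3. **What follows in that branch.** The premedication sentence is not restricted to patients without a recurrence. Read in sequence, it leaves week 4 open.
4. **The same event in the next bullet.** Return of symptoms after initial improvement is a separate Grade 3 feature and need not be accompanied by the other two. Full resolution is a form of improvement, so the patient in step 2 meets it.
5. **Consequence of Grade 3.** Both 7.3 and 7.2.2 require permanent discontinuation, the latter for all study drugs.
6. **Search for a tie-breaker.**
   - 7.2.1 mentions reactions that have not settled within an hour of stopping the infusion, not recurrence.
   - The clause in 7.3 that permits local modification concerns treatment recommendations; it neither ranks the bullets nor overrides 7.2.2.
   - 8.1 item 3 enforces any discontinuation requirement but does not say that this event is Grade 3.
   - SAP 4.3.3 summarises discontinuation without mentioning infusion reactions.

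   None of these settles the grade.

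**Was the restart pathway used?** The protocol calls the Cohort 2 reactions mild. Its own Grade 1 description excludes intervention, and these patients received steroids and had the infusion resumed, so they fit the Grade 2 description. This shows that restarts occurred; it does not show that any symptoms returned.

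**Reach.** Each patient has two planned infusion visits (weeks 0 and 4). After a recurrence at the first, 2 − 1 = 1 infusion visit remains; after a recurrence at the second, none remains. Section 12.1.5 describes Cohort 1 dosing in the past tense, so an amendment affects Cohort 2 only. The planned Cohort 2 size is 24 and the number still awaiting a second dose is not stated, so the range is 0 to 24 patients.

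**The case against.** The strongest reply is that the protocol already resolves the matter. Section 7.2.2 is mandatory, 7.3 offers recommendations, and 8.1 item 3 stops therapy for any discontinuation requirement. On this view the quoted sentence is a bedside step, silent about week 4, and the premedication sentence is general advice that also appears under Grade 1. Much of this stands: the Grade 2 branch does not order re-dosing, and a careful investigator would probably apply the stricter rule. But that rule applies only once the event is graded 3, and the text places the recurrence step under Grade 2 without directing a regrade.

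A second reply is that return of symptoms on re-exposure after full resolution differs from return after partial improvement. This is a possible reading but a strained one, since the Grade 3 phrase draws no such line.

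A third reply is that severity is graded by CTCAE v5.0 whichever management branch is followed (Protocol 7, 7.3 and 9.1). This reply succeeds against a stronger reading. A reader might infer that the layout of 7.3 will understate the primary endpoint or cause 24-hour reports to be missed. Where a step is printed does not set the recorded grade, and both consequences follow the grade. One patient in Cohort 2 is 1/24 = 4.2 percentage points, but the documents give no count of misgraded patients to apply it to. Nor can the interim suspension rule be affected by whether such a reaction is graded 2 or 3, because 5.4 and 13.1.1 exclude Grade 3 infusion reactions.

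**Conclusion.** The inconsistency is real and should be corrected. Section 7.3 gives two incompatible instructions for recurrence after restart, and one of them conflicts with 7.2.2. The matter is patient safety and consistent dosing; sample size, power and analysis are untouched. Its size is at most one avoidable re-exposure visit per affected patient, among the 0 to 24 Cohort 2 patients not yet given a second dose. If all second doses have been given, an amendment can no longer change dosing.

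The conclusion assumes that the reaction is drug-related, as 7.2.2 requires, and that return of symptoms after resolution falls within the printed Grade 3 wording. CTCAE v5.0 itself is not among the documents, so the point rests on the protocol's own grade descriptions. It would be wrong to infer that any patient was re-dosed against the rules: the documents report restarts but no recurrence.

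**What to change.** After the quoted sentence in the Grade 2 branch of 7.3, add: *Recurrence after restart meets the Grade 3 definition below: grade as Grade 3, report within 24 hours and permanently discontinue all study drugs per 7.2.2.* Limit the premedication sentence in that branch to Grade 2 reactions without recurrence.

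If the sponsor would rather allow a second dose after a brief recurrence, 7.2.2 needs an explicit exception. The stricter option is preferable because it applies a rule that the protocol already states.

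The cost is one sentence and one limiting phrase. Because the stopping instruction changes, this belongs in the next amendment with the documented sponsor and IRB approval that 15.1 requires; a memo to sites is not enough. The clinical price is that a patient whose reaction recurs but is otherwise moderate forgoes the second of two doses, which 7.2.2 already requires for Grade 3.
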